### 7.2 Investigational Product

Opaganib [3-(4-chlorophenyl)-adamantane-1-carboxylic acid (pyridin-4-ylmethyl)amide, hydrochloride salt] is an orally available inhibitor of the enzyme sphingosine kinase-2 (SK2) (French, 2010). SK2 is an innovative molecular target due to its critical role in sphingolipid metabolism, which is known to regulate many cellular functions, including the replication-transcription complex (RTC) of +single-strand RNA viruses (Reid, 2015).

### 7.3 Preclinical Rationale

Recent pre-clinical studies *in vitro* data demonstrate that opaganib completely inhibits viral replication of SARS-CoV-2, at concentrations that are achievable in human serum. . Working in collaboration with the University of Louisville Center for Predictive Medicine and Biodefense, opaganib was studied in a 3D tissue model of human bronchial epithelial cells (EpiAirway™, HBEC) which morphologically and functionally resembles the human airway and is similar to the model used to discover SARS-CoV-2. This study was designed to evaluate the *in vitro* efficacy of opaganib in inhibiting SARS-CoV-2 infection and included a positive control of remdesivir, a drug with known antiviral activity. Results from this study showed a clear and compelling effect of opaganib resulting

in complete inhibition of SARS-CoV-2 viral replication (Figure 1). Treatment of cells infected with SARS-CoV-2 resulted in a dose-dependent inhibition of infectious virus production without compromising cell membrane integrity, a measure of cell viability and drug safety, demonstrating opaganib's promising potential for treating patients with COVID-19 (Figure 2)

Figure 1.

[figure not shown]
[figure not shown]

Figure 2.

Additionally, preclinical studies demonstrate that opaganib both inhibits host inflammation and has anti-viral properties. Using SK2-/- mice and differential gene expression analysis, it was demonstrated that SK2/sphingosine-1-phosphate (S1P) signaling could play a key role in promoting pneumonia via promoting inflammation and suppressing other factors that inhibit inflammation and host defense (Ebenezer, 2019). The results suggested that inhibition of SK2 may both inhibit viral replication and decrease pulmonary inflammation, ameliorating lung injury. Additional evidence for the anti-inflammatory properties of opaganib is derived from murine inflammatory bowel disease (IBD) models of ulcerative colitis, Crohn's disease and rodent models of inflammatory arthritis and liver ischemia reperfusion. Opaganib has been shown to suppress anti-inflammatory responses in-vitro and in-vivo, including:

- 1) decreased IL-6 levels, TLR4 expression, NF-κB activation and TNF $\alpha$ -induced activation of NF $\kappa$ B pro-inflammatory cytokine/ chemokine (TNF $\alpha$ , IL-1 $\beta$  and CXCL-10) production (Liu, 2010, Maines, 2008, Maines, 2010)
- 2) decreased infiltration of monocytes/ macrophages and neutrophils ( Liu, 2012)
- 3) blocked CD4+ T cell infiltration and IFN $\gamma$  production (Liu, 2012)
- 4) abrogation of TNF $\alpha$ -induced expression of adhesion proteins and blockade of TNF $\alpha$ -induced PGE2 as a measure of COX-2 activity (Maines, 2008).

Several other studies have reported that SK2 regulates cellular gene expression during Chikungunya virus (CHIKV) infection (Reid, 2015) and can maintain viral latency for Kaposi's sarcoma-associated herpesvirus (Dai, 2014). SK2 recruitment into the RTC has been demonstrated in CHIKV in the Togaviridae family of viruses which contains a non-segmented +single stranded RNA genome (COVID-19 is a +single stranded RNA genome). Treatment of infected HepG2 cells with opaganib

significantly reduced CHIKV infection (Reid, 2015). Targeted knockdown of SK2 also inhibited hepatitis c virus (HCV) replication (Yamane, 2014).

Inhibition of SK2 with opaganib has also demonstrated a decrease in viral titers of influenza virus in an in vitro model system (with an EC50 well within the achievable concentrations of opaganib in humans, based on the phase 1 human trial) as well as improved survival in a preclinical study of influenza infected mice receiving opaganib daily for two days (Xia, 2018).

Opaganib has also demonstrated a substantial inhibitory effect in a dose dependent manner in a preliminary Ebola cell-based inhibition assay (RedHill Biopharma, unpublished data). The doses that displayed near complete inhibition of Ebola cellular infection are also achievable in humans.

## 7.4 Prior Clinical Experience

To date, four clinical trials have been completed with opaganib, a phase 1 food and administration route effect study in healthy volunteers, a phase 1b study in advanced solid tumor patients, a phase 1b/2 study in patients with advanced multiple myeloma and a Phase 2a study evaluating opaganib in patients with moderate-to-severe SARS-CoV-2 infection.. Two additional studies are currently in progress, a phase 2 study in patients with cholangiocarcinoma and a phase 2 study in patients with castration-resistant prostate cancer. Based on the Phase 1b studies, described in Section 7.4.1.1 and Section 7.4.1.2, based on safety and tolerability, the dose of 500 mg of opaganib every 12 hours was selected for future studies. The duration of treatment in oncology patients has been considerably longer than that proposed for COVID-19 patients, with oncology patients receiving opaganib daily for more than 2 years.

### 7.4.1 Completed Studies

#### 7.4.1.1 Phase 1b Study in patients with advanced solid tumors (Study No. ABC-101)

Twenty-two patients were enrolled, of whom 21 were treated with doses from 250 mg QD through 750 mg BID. All 21 patients were evaluable for pharmacokinetics, pharmacodynamics and safety. Sixteen were evaluable for efficacy per RECIST 1.1 criteria. Patients received treatment continuously in 28 day cycles and treatment was given while fasting. Mean age of patients entered was 58 years. Seventy one percent were male, 67% white. All patients had received prior chemotherapy and approximately half had prior surgery and/or radiotherapy. Patients had a variety of concomitant medical conditions and were receiving a variety of medications in addition to their antitumor therapy.

The administered oral dose of 500 mg Q12 hours was the maximum tolerated dose. There were no deaths reported during the administration of opaganib. There were no discontinuations due to adverse events (AEs), in 250 mg QD and 250 mg bid cohorts. Common adverse events were nausea (12 patients, 57%), fatigue (12 patients, 57%), vomiting (8 patients, 38%) and neuropsychiatric effects (14 patients, 67%) including anxiety, insomnia, agitation and dysarthria. Of these, only fatigue appeared to be dose-related. Nausea and vomiting were common but not dose-limiting and rarely required discontinuation of treatment. Neuropsychiatric effects were seen at all dose levels, though were more common and bothersome at the highest dose level, 750 mg Q12 hours, considered an intolerable dose.

There were no consistent trends toward increases or grade shifts in liver function tests, hematologic parameters, or other biochemical parameters except for creatinine and lymphocytes. No patient developed clinically significant ECG abnormalities on study. There were no treatment group differences noted for the changes from baseline of QTcF. For more detailed data refer to Investigator Brochure.

#### **7.4.1.2 Phase 1b Study in patients with advanced multiple myeloma (Study No. ABC-103)**

Thirteen patients received study drug: 3 at 250 mg Q12 hours, 4 at 500 mg Q12 hours and 6 at 750 mg Q12 hours. Median age of patients was 69 years (range 57-89), 7 were males, 7 were white and 6 black. All patients had received multiple courses of therapy with a median of 7 prior lines of treatment (range 3-13) excluding stem cell transplantation. Eight patients had autologous hematopoietic stem cell transplantation.

The administered oral dose of 500 mg Q12 hours was the maximum tolerated dose. There were no deaths reported during the administration of opaganib. Common adverse events included dyspepsia, nausea and vomiting. Eight patients experienced neuropsychiatric effects including altered mental state, confusion, dizziness, hallucinations and insomnia. All patients experiencing neuropsychiatric effects were receiving concomitant narcotic analgesics and several patients were also receiving other psychotropic medications. In several patients, after adjustment of the narcotic analgesic dosing regimen, the symptoms subsided, with maintenance or improvement of pain control. For more detailed data refer to Investigator Brochure.

#### **7.4.1.3 Phase 1a Study of food and administration route effect study in healthy volunteers (Study No. ABC-109)**

A total of 23 subjects participated in the study, 19 each received the drug orally in the fed and fasted states, and 21 via nasogastric (NG) tube. Mean and median ages of the subjects were 48.2 and 50.0 years, respectively (range 22-72 years). Of the subjects, 56.5% were males, 78.3% were white, and 47.8% were Hispanic. Median weight was 75.2 kg (range 52.0-123.3).

Subjects received a single 500 mg dose of opaganib (two 250 mg capsules) after a large standard meal, while fasting, and via nasogastric tube. Overall, 13 subjects (56.5%) experienced at least one treatment-emergent event (TEAE). Of these, 9/13 and 4/13 experienced a Grade 1 and Grade 2 TEAE, respectively.

Overall, the most common TEAEs were nausea (3 subjects, 13%), diarrhea (3 subjects, 13%), dizziness (5 subjects, 21.7%) and headache (5 subjects, 21.7%). The drug was better tolerated after food as compared to the fasting state, with double the proportion of subjects experiencing TEAEs after fasted administration of opaganib compared to the fed state.

Administration with a large standard meal (fed state) resulted in prolongation of absorption, with an increase in time to maximum concentration by one hour and a 43% decrease in peak plasma concentration. Overall bioavailability (AUC0-inf) was reduced by 17% compared to fasted state. The change in bioavailability did not appear to affect pharmacologic activity, as S1P suppression, a

pharmacologic consequence of SK2 inhibition, was somewhat higher after administration of opaganib in the fed state.

Administration of an opaganib suspension by nasogastric tube after tube feeding did not substantially alter bioavailability of the drug. Hence, subjects/patients who are unable to swallow capsules may take the drug in suspension form and via NG tube. For more detailed data refer to Investigator Brochure.

#### **7.4.1.4 A Phase 2a (Proof of Concept) Study in patients with moderate to severe COVID-19 Pneumonia (Study No. ABC-110)**

A Phase 2a Proof of Concept study was completed in the US evaluating 40 patients (mITT population) with moderate to severe COVID-19 pneumonia (aligning with WHO Ordinal Scale of Improvement Scores of 4 and 5) (NCT04414618). The primary endpoint was a comparison of the AUC for supplemental oxygen requirements in opaganib treated vs. placebo control patients over the 14 day treatment period. All participants received 500 mg of investigational product Q12 hours for 14 days, unless they were discharged prior to 10 days, in which case they continued treatment to a total of 10 days. The investigational product, either opaganib 500 mg Q12 hours or matching placebo, was given on top of standard of care therapy. Secondary endpoints included several metrics for supplemental oxygen requirement, intubation and mortality. The study was intended as a proof of concept study and was not powered to detect a difference in the efficacy measurements.

The preliminary results demonstrated that opaganib as compared to placebo led to improved time to 50% reduction of supplemental oxygen requirement; a greater percentage of patients no longer needing supplemental oxygen by Day14 of treatment and less total oxygen requirements during the 14 days of treatment, as measured by Area under the curve (AUC). Further evaluations showed a greater percentage of patients on opaganib no longer needed supplemental oxygen by Day 7 and had improved time to discharge from hospital, compared to placebo.

#### **7.4.1.5 Compassionate Use Experience**

Under compassionate exemption, 7 patients with severe COVID-19 infections have been treated with opaganib. These results are uncontrolled however provide important clinical data within the compassionate use context. One patient improved 36 hours after initiation of treatment to room air and was discharged from hospital. Five other patients were treated with opaganib for up to 14 days. All patients had clinical improvement and were discharged from hospital. Patients treated with opaganib in the compassionate use program did not progress to requiring intubation and mechanical ventilation. Patients receiving opaganib via compassionate use were compared to a matched case-control group of 18 patients (Kurd, 2020). Opaganib treated patients had faster improvement in lymphocyte counts, decreased CRP and faster time to being weaned off high flow oxygen. Of the 18 match controls, 6/18 cases required intubation and mechanical ventilation.

One patient started hydroxychloroquine, azithromycin and opaganib within 24 hours and had diarrhea necessitating withdrawal of all three medications. This was the only adverse event thought to be at least possibly related to opaganib.

## 8 RATIONALE FOR OPAGANIB IN COVID-19

Opaganib has demonstrated substantial anti-viral effects for RNA viruses in pre-clinical models. Opaganib has demonstrated the ability to completely inhibit SARS-CoV-2 infection in a bronchial epithelial *in vitro* model and has suggested several aspects of clinical benefit in the ABC-110 clinical trial described above.

However, like all other experimental treatments at this time, opaganib has not been proven to be better or worse than the currently approved COVID-19 medicines. In this regard, its place among the existing experimental medicines will be at the discretion of the study physician, based on the pharmacological action described above, existing data and dosage form. Of note, in patients who are unable to swallow capsules, opaganib made into a suspension form (refer to Section 12.6) may be administered via a nasogastric tube (administering opaganib suspension via nasogastric tube did not substantially alter the bioavailability of opaganib after a tube feed in a healthy volunteer study).

The population to be enrolled in this study will have severe COVID-19 infection, be hospitalized and require supplemental oxygen to treat hypoxemia, with or without an increased work of breathing. The effect of opaganib, as an anti-viral and anti-inflammatory medicine, if effective, is likely to provide the most measurable benefit at this clinical stage of severity.

## 9 STUDY OBJECTIVES

### 9.1 Primary

To evaluate the proportion of patients no longer requiring supplemental oxygen for at least 24 hours by Day 14

### 9.2 Secondary

- 1) To evaluate change on the WHO Ordinal Scale for Clinical Improvement
- 2) To evaluate the time to recovery defined by improvement to a score of 3 or less on the WHO Ordinal Scale for Clinical Improvement
- 3) To evaluate the time to low oxygen flow via nasal cannula e.g. from high oxygen flow via nasal cannula or positive pressure ventilation at baseline
- 4) To evaluate time to discharge from the hospital
- 5) To evaluate the proportion of patients requiring intubation and mechanical ventilation by Day 42
- 6) To evaluate the time to two consecutive negative swabs for SARS-CoV-2 by PCR
- 7) To evaluate the proportion of patients with two consecutive negative swabs for SARS-CoV-2 by PCR at Day 14
- 8) To evaluate the proportion of patients, with at least one measurement of fever at baseline (defined as temperature  $>38.0\text{ C}$  [ $100.4\text{ F}$ ]), who are afebrile (defined as temperature  $<37.2\text{ C}$  [ $99\text{ F}$ ]) at Day 14
- 9) To evaluate mortality 28 and 42 days post-baseline

### 9.3 Exploratory

- 1) To assess the change in systemic markers of inflammation (D-dimer, cardiac troponin, C-reactive protein [CRP], lactate dehydrogenase [LDH] and ferritin) over the treatment period of 14 days
- 2) To assess the change in lymphocyte count over the treatment period of 14 days
- 3) To evaluate the time to recovery defined by improvement to a score of 1 or less on the WHO Ordinal Scale for Clinical Improvement
- 4) To evaluate the proportion of patients no longer requiring supplemental oxygen for at least 24 hours by Day 7
- 5) To evaluate time to 50% reduction of supplemental oxygen requirement for the subset of subjects who do not require positive pressure ventilation during the study

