### 11.2 Exclusion Criteria

- 1) Any co-morbidity that may add risk to the treatment in the judgment of the investigator, particularly patients with known cardiac conditions, and serious neuropsychiatric conditions such as psychosis or major depression.
- 2) Requiring intubation and mechanical ventilation at baseline

- 3) has a 'Do Not Intubate' and/or 'Do Not Resuscitate' order in place
- 4) Oxygen saturation >95% on room air
- 5) Any preexisting respiratory condition that requires intermittent or continuous ambulatory oxygen prior to hospitalization
- 6) Patient is, in the investigator's clinical judgement, unlikely to survive >72 hours
- 7) Pregnant (positive serum or urine test within 3 days prior to randomization) or nursing women
- 8) Unwillingness or inability to comply with procedures required in this protocol.
- 9) Corrected QT (QTc) interval on electrocardiogram (ECG) >470 ms for females or >450 ms for males, calculated using Friedericia's formula (QTcF)
- 10) AST (SGOT) or ALT (SGPT) > 2.0 x upper limit of normal (ULN)
- 11) Total bilirubin >1.5 x ULN (except where bilirubin increase is due to Gilbert's Syndrome)
- 12) Serum creatinine >2.0 X ULN
- 13) Absolute neutrophil count <1000 cells/mm^3
- 14) Platelet count <75,000/mm^3
- 15) Hemoglobin <8.0 g/dL
- 16) Medications that are sensitive substrates, or substrates with a narrow therapeutic range, for CYP1A2, CYP2B6, CYP2C8, CYP2C9, CYP2C19 CYP2D6 , CYP3A4, P-gP, BCRP and OATP1B1 should be avoided with opaganib. Please see Appendix 2
- 17) Moderate or strong inhibitors of CYP1A2, CYP3A4, CYP2D6 or P-gP or moderate to strong inducers of CYP3A4 and CYP1A2 are prohibited. Please see Appendix 2
- 18) Currently taking warfarin, apixaban, argatroban or rivaroxaban due to drug-drug interaction based on CYP450 metabolism. For washout periods, refer to Section 13.1.4.
- 19) Current drug or alcohol abuse
- 20) Currently participating in a clinical study assessing pharmacological treatments, including anti-viral studies.

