## 12 STUDY DESIGN

### 12.1 Overall Investigation Plan

This is a phase 2/3 multi-center randomized, double-blind, parallel arm, placebo-controlled study, with an adaptive design that will utilize a futility assessment. The study is planned to be performed worldwide in approximately up to 80 clinical sites.

After informed consent is obtained, patients will enter a screening phase for no more than 3 days, to determine eligibility. Approximately 464 eligible patients will be randomized and receive either opaganib added to standard of care, or matching placebo added to standard of care, in a randomization ratio of 1:1. Treatment assignments will remain blinded to the patient, investigator and hospital staff, as well as the sponsor.

Study participants will receive either opaganib 2 x 250 mg capsules (500 mg) every 12 hours, or matching placebo, in addition to standard of care (pharmacological as defined above and/or supportive) at any given institution. Study drug will be administered every day for 14 days (Day 1 to Day 14).

All participants will be followed up for 42 days after their first dose of study drug. The maximum duration of study participation will be up to 45 days (including up to 3 days screening; up to 14 days of double-blind treatment and completion of study at Day 42).

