### 15.2 Secondary

- 1) The percentage of patients with  $\geq 2$  category improvement on the WHO Ordinal Scale for Clinical Improvement by Day 14 for the opaganib arm as compared to the placebo arm
- 2) Time to recovery as defined by improvement to a score of 3 or less on the WHO Ordinal Scale for Clinical Improvement for the opaganib arm as compared to the placebo arm
- 3) Time to low oxygen flow via nasal cannula e.g. from high oxygen flow via nasal cannula or positive pressure ventilation at baseline
- 4) The time to discharge from the hospital for the opaganib arm as compared to the placebo arm
- 5) The percentage of patients requiring intubation and mechanical ventilation by day 42 for the opaganib arm as compared to the placebo arm
- 6) The time to two consecutive negative swabs for SARS-CoV-2 by PCR, at least 24 hours apart for the opaganib arm as compared to the placebo arm
- 7) The percentage of patients with at least two consecutive negative swabs for SARS-CoV-2 by PCR at Day 14 for the opaganib arm as compared to the placebo arm
- 8) The percentage of patients with at least one measurement of fever at baseline (defined as temperature  $>38.0$  C [100.4 F]), who are afebrile (defined as temperature  $<37.2$  C [99 F]) at Day 14 for the opaganib arm as compared to the placebo arm
- 9) Mortality due to any cause at Days 28 and 42 after baseline for the opaganib arm as compared to the placebo arm

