### 15.3 Exploratory

- 1) The change in systemic markers of inflammation (D-dimer, cardiac troponin, C-reactive protein [CRP], lactate dehydrogenase [LDH] and ferritin) from baseline at Day 14
- 2) The mean change in lymphocyte count from baseline at Day 14 for the opaganib arm as compared to the placebo arm
- 3) Time to recovery as defined by improvement to a score of 1 or less on the WHO Ordinal Scale for Clinical Improvement for the opaganib arm as compared to the placebo arm
- 4) The percentage of patients no longer requiring supplemental oxygen for at least 24 hours by Day 7 for the opaganib arm as compared to the placebo arm
- 5) The time to 50% reduction of supplemental oxygen requirement for the subset of subjects who do not receive positive pressure ventilation (non-invasive or invasive) for opaganib arm as compared to the placebo arm

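### Exploratory endpoint 5 selects patients by whether they are ventilated after randomisation, so its two arms are no longer comparable; define the subset at baseline instead (minor)

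*Protocol*

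**What the plan says.** Protocol Section 9.3, objective 5, evaluates time to a 50% reduction in oxygen requirement "for the subset of subjects who do not require positive pressure ventilation during the study". The matching endpoint in Section 15.3 limits the analysis to patients who "do not receive positive pressure ventilation (non-invasive or invasive", closing the bracket there and naming no time window. The synopsis repeats each wording once, under exploratory objectives and under exploratory endpoints.

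Four other places bear on how this is read:

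- Section 11.2, criterion 2, excludes patients "Requiring intubation and mechanical ventilation at baseline". Section 11.1, criterion 3, admits patients on non-intubated positive pressure support.
- Section 15.2, endpoint 5, is "The percentage of patients requiring intubation and mechanical ventilation by day 42 for the opaganib arm as compared to the placebo arm".
- Section 12.1: "All participants will be followed up for 42 days after their first dose of study drug".
- Section 19.5 sets Day 1 to Day 14 as the default time frame for time-to-event endpoints and, for recovery-type events, censors deaths at the end of the frame. That section is written for the secondary endpoints.

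**The concern.** The subset cannot be read as a baseline subset. The objective refers to the whole study. Intubated patients cannot enter, so the invasive part of the endpoint's condition can only be met after entry. Membership therefore depends on each patient's later course, which the drug is meant to influence: intubation is a secondary endpoint, and the background in Section 7.4.1.5 reports that compassionate-use patients "did not progress to requiring intubation and mechanical ventilation" whereas among matched controls "6/18 cases required intubation and mechanical ventilation".

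If the drug keeps some patients off ventilation, they stay in the opaganib subset while their counterparts are dropped from the placebo subset. Such patients are probably sicker and slower to wean, so the opaganib subset would look worse for a reason that is a benefit. If the drug led to more ventilation, the opaganib subset would lose its sicker patients and look better.

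The window adds to the problem. A patient who halves the oxygen requirement on Day 5 and is ventilated on Day 20 would be removed, under the objective's wording, by an event that follows the outcome being measured.

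At stake is the reading of an oxygen-weaning measure that Section 7.4.1.4 names first among the favourable Phase 2a results, so readers are likely to look to it for confirmation.

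**Working it through.** **The plan's own figures.** The protocol gives no rate, effect or power for this endpoint. Its primary sample size is not in dispute and reproduces: 40% versus 55% at two-sided 0.05 and 90% power needs 231 per arm (462 in total, against the stated 464), and 232 per arm gives 90.1% power.

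**Assumed inputs (none is in the protocol).**

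- v0, v1: proportion ever on positive pressure ventilation, placebo and opaganib.
- pm = 70%: Day 14 rate of 50% oxygen reduction in patients who avoid ventilation on either arm.
- ps: the same rate in patients kept off ventilation only by the drug, varied from 20% to 70%.
- No direct effect of the drug on weaning. Any difference inside the subset is then pure selection.

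The 6/18 = 33% in matched controls is the only ventilation figure in the document. It covers intubation only and comes from outside this trial, so it is context and not an input.

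**Formulas.** The share of rescued patients in the opaganib subset is w = (v0 − v1)/(1 − v1).

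- Subset: placebo pm; opaganib (1 − w)·pm + w·ps.
- All patients, ventilation counted as not reached: placebo (1 − v0)·pm; opaganib (1 − v0)·pm + (v0 − v1)·ps.

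**Base case, 30% versus 20%, ps = 20%.** w = 0.10/0.80 = 0.125. Opaganib subset: 0.875 × 70 + 0.125 × 20 = 63.75%, against 70% on placebo, a difference of −6.25 points. All patients: 0.70 × 70 = 49.0% against 49.0 + 0.10 × 20 = 51.0%, a difference of +2.0 points. Of 232 randomised per arm, the subsets hold about 162 and 186.

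| Ventilation, placebo vs opaganib | ps | Subset difference (points) | All-patient difference (points) |
|---|---|---|---|
| 30% vs 20% | 20% | −6.25 | +2.0 |
| 30% vs 20% | 40% | −3.75 | +4.0 |
| 30% vs 20% | 60% | −1.25 | +6.0 |
| 30% vs 20% | 70% | 0 | +7.0 |
| 30% vs 10% | 20% | −11.1 | +4.0 |
| 40% vs 20% | 20% | −12.5 | +4.0 |
| 40% vs 20% | 40% | −7.5 | +8.0 |

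With exponential times to reduction and follow-up cut at Day 14, the base case gives a hazard ratio of about 0.86 in the subset and 1.06 with all patients. For 40% versus 20% at ps = 20% they are 0.74 and 1.11. The bias vanishes only when ps = pm.

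**Opposite direction.** Swapping the arms of the base case (20% ventilated on placebo, 30% on opaganib) gives 63.75% versus 70%, or +6.25 points in favour of a drug that causes escalation.

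**Adding a direct weaning effect.** Suppose the drug also raises pm from 70% to 85% (the 15 points are borrowed from the primary endpoint's assumption, and ps is left at 20%).

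- 30% versus 20%: 0.875 × 85 + 0.125 × 20 = 76.9%, or +6.9 points. This is attenuated from 15, not reversed.
- 40% versus 20%: 0.75 × 85 + 0.25 × 20 = 68.75%, or −1.25 points.

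The subset difference is zero when the opaganib rate in never-ventilated patients is (70 − 0.125 × 20)/0.875 = 77.1% in the first case and (70 − 0.25 × 20)/0.75 = 86.7% in the second.

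**The case against.** The best defence is about measurement and rank. Oxygen requirement is recorded as flow in L/min, and halving a flow is hard to define under positive pressure, so some restriction is reasonable. The protocol does not give this reason. It supports excluding patients already on such support at baseline, a legitimate restriction. It does not support removing patients who escalate later, because they can stay in the analysis without a flow value under ventilation.

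The weaning question is also asked without this restriction by the primary endpoint, secondary endpoints 2 and 3 and exploratory endpoint 4, and differences in intubation and death are reported as secondary endpoints 5 and 9. That stands, and it limits the harm. It does not repair this endpoint.

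Two stronger readings are tempting. A reader might infer that the endpoint will show an effective drug as harmful. The documents do not support that: the reversal above needs an effect on ventilation, slower weaning in rescued patients and little or no direct weaning effect, and the protocol supplies none of those rates for this trial. A reader might also infer that the trial's conclusions are at risk. They are not: Section 19.7 confines formal testing to the primary endpoint and the secondary hierarchy, and Section 19.8 bases futility on the primary and key secondary endpoints.

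Finally, the all-patient figures are not a corrected estimate of the same quantity. With no weaning effect assumed, the +2 points merely restate the assumed ventilation benefit. Counting any ventilation as permanent failure would also fail a patient who has brief non-invasive support and then weans.

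**Conclusion.** The point holds as a minor one. As worded, exploratory endpoint 5 conditions on a post-randomisation event that treatment may change, and no other part of the protocol restores comparability for it. The subset definition is fixed in the protocol itself, so it is not a detail left to the SAP. The direction of bias depends on the drug's effect on ventilation: against the drug if it prevents ventilation and rescued patients wean more slowly, in its favour if it causes escalation. Under the assumed rates with no direct weaning effect, the bias against the drug runs from 0 to 12.5 points; these figures show the mechanism and do not predict the result.

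**What to change.** In Sections 9.3 and 15.3 and in both synopsis entries, define the subset as mITT patients not on positive pressure ventilation before the first dose, and keep all of them in the analysis. The same edit removes the mismatch between requiring and receiving ventilation.

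Add a handling sentence, since Section 19.5 is written for secondary endpoints. A patient is counted as not having reached the reduction while on positive pressure ventilation, and deaths are censored at the end of the time frame, as Section 19.5 does for recovery-type endpoints. Counting any ventilation as not reached, or as a competing event, can be a sensitivity analysis.

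The cost is four short wording changes and one added sentence. No new data should be needed, because the present definition already requires ventilation status throughout the study. The daily WHO level alone will not supply it, since level 5 pools non-invasive ventilation with high-flow oxygen, so confirm that the eCRF separates them.
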